6.3 Quantitative Outcome Measures

Quantitative outcome measures will be assessed in Aim 2 through baseline and follow-up assessments.

Primary Outcome Measures: The primary outcome is PrEP initiation, measured by the number of participants who successfully initiated PrEP during the 8-week intervention period.

Secondary Outcome Measures: Secondary outcomes include self-report PrEP use self-efficacy, PrEP stigma, PrEP adherence (among those who are on PrEP), sexual risk behaviors, sexually transmitted infection incidence, general stress and HIV-related stress.

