1.0 OBJECTIVE

1.1 Hypothesis

We hypothesize that in our study sample, adult men who have sex with men (MSM) in the intervention arm are more likely to report successful PrEP initiation at the end of trial, as compared to the control arm.

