1.3 Secondary Objectives

Secondary objectives include: in our study sample,

- (1) Test the efficacy of the mini-app in decreasing PrEP stigma and increasing PrEP use self-efficacy at the individual level.
- (2) Identify the predictors associated with successful PrEP initiation during the study period.
- (3) Investigate the association between depression at baseline and successful PrEP initiation during the study period.
- (4) Assess PrEP use adherence among participants who successfully started PrEP during the study period.

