In addition to Web-based surveys, a subgroup of participants (n=20) from both the intervention arm and the control arm will receive up to two rounds of in-depth interviews, separately at the 4th and 8th week, to share their experience of using the app and changed perceptions and/or behaviors related to PrEP. Among the 20 participants, 15 will be recruited for interviews during the first and fourth weeks, who will receive two rounds of interviews. Another five participants will be recruited between the 4th and 8th week, who will be only interviewed once at the 8th week. Interview topics include participants' experience of using the app and changed perceptions and/or behaviors related to PrEP and HIV prevention practices during the study period. Interviews will be conducted one-on-one in private spaces, last 60-90 minutes and will be audio recorded with participant's permission.

Referrals

In the case of an initial positive HIV test done through the study, participants who have initiated PrEP will be instructed to discontinue PrEP dosing. Participants testing positive will be referred to the Guangzhou No.8 People's Hospital for confirmation test or other testing places if needed. The Guangzhou Center for Diseases Prevention and Control will be notified of confirmed positive results in accordance with China's public health reporting laws, a procedure that will be explained to participants at consent. For positive syphilis testing results, participants will be referred to STI treatment at the Guangzhou No.8 People's Hospital. The study team will follow-up with participants testing positive for HIV or STIs to encourage participants to seek appropriate care.

[figure not shown]

Figure 2. Flowchart of Aim 2 study design

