8.2 Endpoints

The endpoint for primary outcome is successful initiation of PrEP.

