8.6 Analyses

Descriptive statistical analysis will be first conducted to report demographic characteristics of participants, PrEP uptake rates, PrEP-related perceptions, PrEP adherence, HIV/STI testing behaviors, prevalence of STIs, mini-app use behaviors at different time points throughout the study period. Statistical tests including Chi-Square tests and t-tests will be conducted to compare the preliminary intervention effects (i.e. the efficacy of mini-app in improving PrEP-related perceptions, increasing PrEP uptake rates and HIV/STI testing behaviors) between the intervention group and control group at each time point. Multivariate logistic regression models will be applied to estimate the association between intervention arm and the primary study outcome, PrEP initiation during the 8-week intervention period. If prognostic factors associated with the primary outcome remain insufficiently balanced through simple randomization, we may adjust for these factors in our models. Potential confounding factors that may be included are perceived HIV infection risk, PrEP self-efficacy and perceived PrEP stigma.

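### The primary outcome names no event that counts as PrEP initiation, gives inconsistent time points, and rests on self-report in an unblinded trial although reimbursed fills could probably be dated to check it

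*Combined protocol and SAP*

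**What the plan says.** **Event.** Section 6.3 counts participants, "measured by the number of participants who successfully initiated PrEP during the 8-week intervention period". Section 8.2 adds nothing operational: "The endpoint for primary outcome is successful initiation of PrEP".

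**Time.** Section 8.6 models "the primary study outcome, PrEP initiation during the 8-week intervention period", in line with 6.3. The hypothesis in 1.1 is that app-arm men are "more likely to report successful PrEP initiation at the end of trial, as compared to the control arm". Section 8.2 gives no time.

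**Source.** Section 6.3: "Quantitative outcome measures will be assessed in Aim 2 through baseline and follow-up assessments". Sections 3.0 and 6.1 make these assessments self-administered web surveys at baseline and weeks 2, 4, 6, 8 and 12. Section 8.1 states that the trial is unblinded.

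**Route to PrEP.** Section 3.0 (PrEP initiation) lets men in both arms choose PrEP until the end of week 8. Contact, referral, examination, prescription (daily or event-driven) and a fill then follow. The study pays for the examinations and reimburses 50% of the first two months of pills, up to 60, when filled at the study hospital's own pharmacy. Neither payment is limited to one arm.

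**Adherence.** Secondary objective 4 (1.3): "Assess PrEP use adherence among participants who successfully started PrEP during the study period". Section 8.6 plans to describe "PrEP adherence, HIV/STI testing behaviors, prevalence of STIs, mini-app use behaviors at different time points throughout the study period". Section 3.0 (Follow-up and Data collection) foresees first two-month use ending as late as week 16; the last survey is at week 12.

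**The concern.** A primary endpoint should let two people with the same data reach the same count. Here they might not. A man who decides late in week 8 may be prescribed before day 56, fill after it and take a first dose later still. The gap between fill and first dose could be widest for event-driven users. If the event is not fixed beforehand, it can be chosen after the data are seen.

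The source matters as well. Men know their arm, and those given an app that promotes PrEP may be readier to report a start than controls. Error of that kind biases the comparison; it does not just add noise. Section 8.4 intends this pilot to supply the effect size for a full trial, so a biased difference would carry forward into that trial's sample size.

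Separately, the later part of the first two months goes unobserved for daily users who start after week 4, which limits what secondary objective 4 can describe.

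**Working it through.** **1. Which event do the documents point to?** Section 1.3 speaks of men who started PrEP. Section 3.0 (Referrals) says that "participants who have initiated PrEP will be instructed to discontinue PrEP dosing". Section 7.0 refers to side effects after initiation. All three imply drug in use, so first dose is the natural reading. None is a definition, and 6.3, 8.2 and 8.6 do not supply one.

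**2. The plan's own timeline.** Latest start, week 8, plus an 8-week daily course: 8 + 8 = 16 weeks. This reproduces the 16 weeks in section 3.0. It fits a start by week 8 but does not show which step is the start.

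**3. How closely do the surveys date a start?** Surveys at weeks 2, 4, 6 and 8 bracket a reported start to two weeks, which is enough for a yes/no outcome at week 8. If the week-8 survey is missed, the bracket runs from week 6 to week 12 and straddles the cut-off. The survey forms are not in the documents and may ask for a date; it would still be self-reported.

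**4. Effect of one misclassified man (40 app, 30 control; section 8.3).**
- App arm: 1/40 = 2.5 points.
- Control arm: 1/30 = 3.3 points.
- One man in each arm, same direction: 3.33 − 2.50 = 0.8 points on the difference.
- One false start in the app arm and one missed start in the control arm: 2.50 + 3.33 = 5.8 points.
- Largest 95% half-width of the difference (both rates 50%): 1.96 × √(0.25/40 + 0.25/30) = 23.7 points.

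**5. Over-reporting in one arm (illustration; every rate is assumed).** Take equal true initiation in both arms, no over-reporting among controls, and 5% to 15% of app-arm non-initiators reporting a start. The rejection rate of a two-sided 5% chi-square test at 40 v 30, by exact enumeration, is then:

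| True rate, both arms | No over-reporting | 5% | 10% | 15% |
|---|---|---|---|---|
| 10% | 4.9% | 8.1% | 17.7% | 32.0% |
| 20% | 5.1% | 6.8% | 11.9% | 20.2% |
| 30% | 5.1% | 6.2% | 9.6% | 15.3% |

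**6. Adherence window for an 8-week daily course.** Weeks observed by the last survey = min(8, 12 − start week).

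| Start week | Seen by week 12 | Seen with a week-16 survey |
|---|---|---|
| 0 to 4 | 8 of 8 | 8 of 8 |
| 5 | 7 of 8 | 8 of 8 |
| 6 | 6 of 8 | 8 of 8 |
| 7 | 5 of 8 | 8 of 8 |
| 8 | 4 of 8 | 8 of 8 |

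Event-driven use has no fixed end, so the table does not apply to it.

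**The case against.** **Fill as the primary event.** A reader might infer that, because a fill can be dated, the fill should replace the survey as the primary event. The documents do not support this. Their wording points to PrEP actually started, and an event-driven user may hold pills for some time before a first dose. Adopting the fill would change what is measured. Adding survey-reported fills from elsewhere would also let self-report back in. This objection stands, and the fill is used below only for verification.

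**Existence of the record.** Section 3.0 describes a half-reimbursement. It mentions no claim form and no link to study ID. That fills can be dated is an inference from the fact that someone must show a fill to be repaid. Section 3.0 also says the team will not see medical records, but explains this as the examination results, so it does not clearly bar a reimbursement log.

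**Size.** The documents give no uptake rate, no lag between steps and no misreporting rate. Error in the same direction in both arms largely cancels. The 5.8-point case and the rejection rates are constructed. It would be wrong to conclude that the result will be biased; the plan only lacks a means of finding out.

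**Week 12.** A reader might infer that stopping surveys at week 12 is a mistake. It is not: the Protocol Summary sets follow-up there expressly, the 16 weeks is tied to app access, and secondary objective 4 does not promise the whole first two months. Even a week-8 starter has four weeks observed. This part is an improvement to consider, not a correction.

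**Conclusion.** The concern holds in a limited form. The qualifying event is undefined, and the time point in 1.1 conflicts with 6.3 and 8.6. The sole stated source is self-report in an unblinded trial, although an apparently available check goes unused. The first two follow directly from the text; the availability of the check rests on the inference about reimbursement.

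The number of men affected is unknown. A single borderline case is small beside the pilot's imprecision. The matter becomes important if several men are affected or if reporting differs by arm, because imprecision does not excuse bias in an estimate meant to size the next trial. The change should be made, with medium confidence in its practical effect. The week-16 survey is a separate and optional gain for a descriptive secondary objective.

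**What to change.** **Primary outcome**
1. State one event and one window, by the end of week 8 (day 56) from enrolment, in 1.1, 6.3, 8.2 and 8.6. Given the protocol's own usage, the event is PrEP actually started; ask for the date of first dose in every follow-up survey.
2. Log study ID and fill date whenever a fill is reimbursed, in both arms alike, and use the log to verify reported starts.
3. Beside the self-reported outcome, report record-confirmed initiation: a reimbursed fill by day 56, with no self-report added.
4. Add a sensitivity count to week 12 for men who chose PrEP by week 8 but completed the steps later.

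**Adherence (optional).** Send initiators in both arms one short survey at week 16, and report adherence by time since start, separately for daily and event-driven users.

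**Cost and limits.** The work is protocol wording, a date question in the surveys and a two-field log. At the existing 5-CNY short-survey rate, the week-16 survey costs at most 70 × 5 = 350 CNY, and section 6.4 would need updating. Both IRBs must approve the changes (9.1), and the consent form may need revision (9.2.6). A fill does not prove a dose. Fills made elsewhere or not claimed stay unconfirmed, so the record-confirmed count may be too low and should be read alongside the self-reported one.

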6.4 Incentives

Aim 1: Remuneration will be provided at the end of each completed interview (total of three possible interviews) in the form of a 75-CNY (~ 10 USD) gift card or equivalent. The participant may opt to stop the interview at any time, however remuneration will only be provided for completed interviews.

Aim 2: Participants in Aim 2 will receive up to 340 CNY in total, including a 50-CNY (~ 7 USD) gift card for the in-person initial visit or baseline assessment at Guangzhou No.8 People's Hospital, and another 20-CNY (~3 USD) gift card for completing each Web-based long follow-up survey at weeks 4, 8, and 12, and 5-CNY (~1 USD) gift card for complete each Web-based short survey at weeks 2 and 6. Participants who are selected for in-depth interviews will receive 75-CNY (~10 USD) gift card for completing each interview (two interviews in total). Remuneration will be provided at the end of each completed session. The participant may opt to stop the interviews/baseline assessment/follow-up surveys at any time, however remuneration will only be provided for completed sessions. Participants who participate in all the required research activities will receive a bonus incentive of 50 CNY at the end of the study.

7.0 PARTICIPANT WITHDRAW AND REPORT

Participants may voluntarily withdraw from the study for any reason at any time. No further data collection will occur from the date the decision is made to permanently discontinue the participant from the study. The study investigators also may withdraw participants from the study in order to protect participant or staff safety. Study staff will record the reasons for all withdrawals.

If a participant fails or is unable to comply with study procedures they will be withdrawn from the study. Participants will be withdrawn if they:

- are noticeably intoxicated or on illegal drugs.
- threaten a study staff member.
- are mentally handicapped and unable to give full informed consent.
- are incarcerated during course of study.
- become HIV-positive during course of study.
- reporting severe medication side effects after initiating PrEP and are advised to quit the study by a HIV specialist.

Any enrolled participant who report any of the above-mentioned events will be immediately stop participation in the study, and study staff will complete a Study Stop form for participants who are discontinued. This form will include the date, last research activity completed, and reason for study discontinuation. These will be reported to the UNC IRB and the Guangzhou No.8 People's Hospital IRB at the end of study.

Reporting is required of all unanticipated problems to the UNC IRB, including those which may occur after the participant has completed or has withdrawn from the study, including after study closure.

Unanticipated problems as defined by the UNC IRB:

Unanticipated problems involving risks to participants or others" or "Unanticipated Problem" refers to any incident, experience, or outcome that:

- is unexpected (in terms of nature, severity, or frequency) given (a) the research procedures that are described in the protocol-related documents, such as the IRB-approved research protocol and informed consent document; and (b) the characteristics of the participant population being studied;
- is related or possibly related to a participant's participation in the research; and
- suggests that the research places participants or others at a greater risk of harm (including physical, psychological, economic, or social harm) related to the research than was previously known or recognized.

Unanticipated Problems that are serious adverse events should be reported to the UNC IRB and Guangzhou No.8 People's Hospital IRB within one (1) week of the investigator becoming aware of the event. Any other Unanticipated Problem should be reported to the UNC IRB and Guangzhou No.8 People's Hospital IRB within two (2) weeks of the investigator becoming aware of the problem. If the Unanticipated Problem Report cannot be completed in its entirety within the required time period, a preliminary report should be submitted. The Unanticipated Problem Report should be amended once the event is resolved and/or more information becomes available.

8.0 STATISTICAL CONSIDERATIONS

This section is only applicable to Aim 2.

8.1 General Design

Aim 2 include a two-arm unblinded RCT, testing the efficacy of a mini-app-based PrEP intervention in promoting PrEP uptake among Chinese MSM compared to standard of care control.

8.2 Endpoints

The endpoint for primary outcome is successful initiation of PrEP.

8.3 Randomization and Stratification

Participants will be simply randomized at initial enrollment visit into two arms (intervention=40, control=30). No stratification will be conducted.

8.4 Sample Size and Accrual

This is a pilot study to test the preliminary efficacy of a WeChat-based mini-app in promoting PrEP uptake rates in an 8-week intervention. Inclusion of a control arm will allow estimation of an effective size to sufficiently power a future full-scale efficacy trial. The full-size intervention study will be designed as a two-arm RCT, following participants up to 12 months and use multilevel modeling methods to understand the association between intervention exposure, changed PrEP perceptions, PrEP initiation and long-term adherence.

8.5 Monitoring

Data will be collected and stored by anonymous identification numbers by study investigators. Data will not be shared with third parties. Data will be discarded 2 years following study completion.

Plans for monitoring participant safety and study progress

The PIs will receive regularly bi-weekly updates from study personnel. In addition, study procedures are established that if at any time during the study a participant divulges that he is at

risk for harm, including but not limited to reporting severe medication side effects, being abused or experiencing violence, if harm is suspected or likely, or if the participant states he is suicidal/homicidal, the PIs will be notified immediately and measures will be taken to ensure the participant's safety. Reporting will be done as appropriate to the situation and the legal statutes, and referrals will be provided for appropriate support, counseling, or treatment resources.

The full study team will hold bi-weekly conference calls to report progress on enrollment, data collection and data analysis. Any challenges that arise will be discussed during these calls and plans made to address.

This study is expected to pose minimal risk. Nevertheless, any unanticipated problems will be recorded in a master log by the PIs and reported during bi-weekly updates (or immediately as described above). The master log will be reviewed during bi-weekly full study team conference calls. Participants may voluntarily withdraw from the study for any reason at any time. Detailed description of participant withdraw and report can be found in section 7.0 in this protocol.

8.6 Analyses

Descriptive statistical analysis will be first conducted to report demographic characteristics of participants, PrEP uptake rates, PrEP-related perceptions, PrEP adherence, HIV/STI testing behaviors, prevalence of STIs, mini-app use behaviors at different time points throughout the study period. Statistical tests including Chi-Square tests and t-tests will be conducted to compare the preliminary intervention effects (i.e. the efficacy of mini-app in improving PrEP-related perceptions, increasing PrEP uptake rates and HIV/STI testing behaviors) between the intervention group and control group at each time point. Multivariate logistic regression models will be applied to estimate the association between intervention arm and the primary study outcome, PrEP initiation during the 8-week intervention period. If prognostic factors associated with the primary outcome remain insufficiently balanced through simple randomization, we may adjust for these factors in our models. Potential confounding factors that may be included are perceived HIV infection risk, PrEP self-efficacy and perceived PrEP stigma.

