Participants in both arms can choose to initiate PrEP at any time point since the initial visit until the end of 8th week. Participants can contact the study team via phone call, text messages or via the chat function in the mini-app to communicate their interest in PrEP initiation. If baseline assessment or follow-up survey results do not show contradictions to PrEP initiation, interested participants will be referred to the Department of Infectious Diseases at Guangzhou No.8 People's Hospital to consult a clinician regarding HIV risks and PrEP eligibility. As is standard of care for any patient starting PrEP, participants will take comprehensive physical examinations (including routine urine examinations, hepatic and renal function tests, blood glucose and lipids, and bone mineral density (BMD)). The study team will not have access to participants' medical records (i.e. the physical examination results). Participants who are confirmed by the clinician HIV-negative, with no serious liver or kidney dysfunction and negative for HBs antigen, without serology indicating osteoporosis, without clinical signs or symptoms consistent with acute viral

infection, will be prescribed either 8-week daily oral TDF/FTC or event-driven oral TDF/FTC based on participants' preference. The cost of physical examinations in order to get PrEP prescription will be covered by the study team. If a participant is eligible for starting PrEP and have been prescribed PrEP by a PrEP provider, the participant will get a 50% reimbursement of the cost for their first two months of PrEP doses (30 pills/month, up to 60 pills in total) filled at the in-house pharmacy of the study hospital (the Guangzhou Eighth People's Hospital).

Follow-up and Data collection

The active intervention period will last for 8 weeks, but participants in the intervention arm can have access to the mini-app throughout the whole study period or until the end of their first two-month PrEP use, which can be as long as 16 weeks. Baseline assessments will be conducted at the enrollment visit, with follow-up assessments conducted at 2, 4, 6, 8, 12 (post-intervention). Participants from both arms will need to complete a self-administrated Web-based survey at each assessment time point.

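### PrEP stigma and self-efficacy are to be compared by t-test at each time point, with no lead week and no stated use of the baseline scores

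*Combined protocol and SAP*

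**What the plan says.** Section 1.3 lists as its first secondary objective: "Test the efficacy of the mini-app in decreasing PrEP stigma and increasing PrEP use self-efficacy at the individual level". Section 6.3 places both scales among the secondary outcomes, attaches no week to them, and says how they are collected: "Quantitative outcome measures will be assessed in Aim 2 through baseline and follow-up assessments".

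Section 8.6 gives the between-arm analysis for PrEP-related perceptions, uptake and testing behaviour together: "Statistical tests including Chi-Square tests and t-tests will be conducted to compare the preliminary intervention effects", made "between the intervention group and control group at each time point". Follow-up surveys fall at weeks 2, 4, 6, 8 and 12 (sections 3.0 and 6.1). Section 6.4 separates the "Web-based long follow-up survey at weeks 4, 8, and 12" from short surveys at weeks 2 and 6. What each survey contains is not stated.

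Section 8.6 then introduces logistic regression for PrEP initiation, followed by the only adjustment clause in the plan: "If prognostic factors associated with the primary outcome remain insufficiently balanced through simple randomization, we may adjust for these factors in our models". It adds: "Potential confounding factors that may be included are perceived HIV infection risk, PrEP self-efficacy and perceived PrEP stigma".

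**The concern.** Only PrEP initiation has a fixed window, the 8-week intervention period. For the two scales the plan does not say which week answers the objective, whether raw or change scores are compared, or what is done with the baseline score of the same scale. The adjustment clause does not fill this gap: it is optional, depends on observed imbalance, and concerns factors prognostic for the primary outcome. In it, stigma and self-efficacy are possible covariates for PrEP initiation. They are not given a role in the comparison of the scales themselves, where a baseline measure of the same scale would be expected to help.

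Two things are at stake. First, section 8.4 says the trial is meant to yield an effect size for a full-scale study, and that the later study will look at changed PrEP perceptions. An estimate that ignores baseline has a wider interval than the collected data allow, and part of any chance baseline difference stays in it. Second, with several weeks tested and none named in advance, the answer to the objective can depend on which survey is read.

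**Working it through.** **Inputs.** From the documents: 40 intervention and 30 control participants; five follow-up surveys, three of them long. Not in the documents, so assumed: two-sided 0.05 per test, complete data, SD set to 1, baseline-to-follow-up correlation r of 0.3, 0.5 or 0.7, and equal correlation between follow-up weeks (rho) of 0.5, 0.7 or 0.9. The plan gives no alpha, power or effect size for these scales, so it has no figure of its own to reproduce.

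**Precision.** The standard error of a raw arm difference is sqrt(1/40 + 1/30) = 0.2415 SD.

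- Raw t-test, 68 df: half-width = 1.995 × 0.2415 = 0.48 SD.
- Baseline-adjusted (ANCOVA), 67 df: half-width = 1.996 × 0.2415 × sqrt(1 − r²).
- Change-score t-test, 68 df: half-width = 1.995 × 0.2415 × sqrt(2(1 − r)).

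| r | Raw | Change score | Adjusted | Variance cut, adjusted v raw (r²) |
|---|---|---|---|---|
| 0.3 | 0.48 | 0.57 | 0.46 | 9% |
| 0.5 | 0.48 | 0.48 | 0.42 | 25% |
| 0.7 | 0.48 | 0.37 | 0.34 | 49% |

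The gain over raw scores is small at r = 0.3. Change scores are worse than raw scores below r = 0.5, and no better than adjustment at any of these values.

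**Chance imbalance.** A baseline difference of one standard error is 0.24 SD. The fraction r of it carries into the raw comparison: 0.3, 0.5 or 0.7 × 0.2415 = 0.07, 0.12 or 0.17 SD. Baseline adjustment removes this shift.

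**Several weeks, no true effect.** The chance of at least one nominally significant week per scale was found by simulation (multivariate normal scores, pooled t-tests, 40 v 30; 200,000 runs, rates agreeing within a few tenths of a percentage point on repetition). The favourable direction means lower stigma or higher self-efficacy in the mini-app arm.

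| Surveys carrying the scale | rho | Either direction | Favourable direction |
|---|---|---|---|
| One named week | any | 5% | 2.5% |
| Three (weeks 4, 8, 12) | 0.5 | 12-13% | 6.3% |
| | 0.7 | 11% | 5.5% |
| | 0.9 | 8-9% | 4.3% |
| Five | 0.5 | 18% | 9% |
| | 0.7 | 15% | 7.5% |
| | 0.9 | 10% | 5% |

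Over three surveys the favourable-direction rate is therefore 1.7 to 2.5 times the single-week rate (4.3/2.5 to 6.3/2.5).

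**The case against.** The strongest reply is that nothing here is invalid. A t-test is unbiased under randomization, the outcomes are secondary, and section 8.4 presents the trial as a pilot for estimating an effect size, where control of multiplicity matters less. The plan states no alpha and no rule that one significant week means efficacy. The list of tests opens with the word including, so adjusted analyses are not excluded. Sections 3.0, 6.3 and 8.6 already call these outcomes secondary or their effects preliminary. All of this stands, and it keeps the point minor. It does not close the gap: a plan that leaves adjusted analyses possible has not committed to one, and a trial run to estimate effect sizes has particular reason to use the baseline data it collects.

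Several stronger readings are tempting, and the documents do not support them:

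- *The scales are tested at all five surveys.* The plan says each time point, but the content of the short surveys is not given. Three tests per scale is the safer count.
- *The risk of a false efficacy claim exceeds 10%.* The two-sided rate counts results favouring control, which nobody would read as efficacy given a directional objective. Even the two-sided rate over three surveys falls to 8-9% at a between-week correlation of 0.9.
- *A chance baseline difference passes whole into the result.* Only the fraction r does.
- *The adjustment clause already covers the scales.* It follows the logistic model and refers to the primary outcome.

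**Conclusion.** The point holds as a minor one. For PrEP stigma and self-efficacy, section 8.6 names only simple between-arm tests at each time point, with no lead week and no use of the scale's own baseline score. The raw 95% CI half-width of 0.48 SD could be 0.46 to 0.34 SD with the same 70 men for r between 0.3 and 0.7, and the benefit is slight at the low end. Over the three long surveys, the chance of at least one falsely favourable week per scale is about 4.3% to 6.3% for between-week correlations of 0.9 to 0.5, against 2.5% for one named week. It is higher if the short surveys also carry the scales.

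These figures rest on an assumed two-sided 0.05, complete data and assumed correlations. The false-positive figures matter only if an isolated significant week is read as efficacy, a rule the plan does not contain. A reader might infer that the planned t-tests are biased or that the analysis of PrEP initiation is compromised; neither follows.

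**What to change.** In section 8.6, for each of the two scales:

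1. Make the arm difference at one pre-specified week, adjusted for that scale's baseline score, the single test. ANCOVA is enough; a mixed model over all surveys carrying the scale, with baseline as covariate, is an alternative. Week 8 is a natural choice: "The active intervention period will last for 8 weeks", and by section 5.0 the reminder messages stop then. The sponsor may justify week 12 instead.
2. Report the other weeks as estimated arm differences with 95% CIs and without significance claims.

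The baseline adjustment should be planned whether or not imbalance is seen. Testing change scores is not a safe substitute, because at low correlation they are less precise than raw scores.

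The cost is a few sentences of analysis text, slightly more analysis work and fewer p-values. No new data are needed, provided the baseline survey and the chosen week's survey both carry the two scales; the plan should say which surveys do.
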